### 9.5 Handling of Missing Data

### 9.5.1 Handling of Missing Efficacy Data

If a patient prematurely discontinues clinical trial participation for any reason apart death, retransplantation or withdrawal of consent, he/she will be encouraged to complete the follow-up. All observed available data will be used for the primary columns analyses. The assumption of the LMM (section 14.1) for missing data will be MAR. Since the definition of progression of BOS includes all relevant intercurrent events (IEs) as failures, drop-outs due to other reasons will be treated as non-informative censoring (section 14.4.2).

Several sensitivity analyses have been planned to assess robustness of primary results in case of deviation from MAR mechanism (sections 14.2).

# 9.5.2 Handling of Missing Safety Data

In general, missing clinical laboratory data, vital signs, and physical examination data will not be imputed. Unknown or partial medication and AE date imputations are given in the next section and to be used only for the assessment of prior/concomitant status for medications and treatment-emergent status for AEs.

# 9.5.3 Handling of Partial and Missing Dates

# 9.5.3.1 Partial and Missing Dates of Birth

Where the Date of Birth is missing the following convention will be used:

Final Version 5.0 Page 30 of 76

- Where the day is missing and month and year are available, the day will be completed as the 15th. For example, Date of Birth specified as --JAN1980 will be completed as 15JAN1980.
- If the day and month are missing and the year is available, the day and month will be completed as 02JUL (the 183rd day of the year). For example, Date of Birth specified as ----1980 will be completed as 02JUL1980.

# 9.5.3.2 Missing or Partial AE and Prior / Concomitant Medication Start and End Dates

Missing and/or incomplete dates for medications and AEs are imputed in a manner resulting in the earliest onset or the longest duration during the Treatment Period, whilst ensuring that the start date does not occur after the stop date.

For the derivation of the duration and cumulative of concomitant medication, if the medication is "Ongoing" then the medication end date will be imputed with the last visit date.

The stop date will not be imputed if the AE is "Ongoing". Technically, this will be done as follows:

- For a missing/incomplete start date/time, the earliest date/time of the following will be imputed:
  - The later date / time of: the earliest possible start date/time and the date/time of first dose of treatment (date/time of randomization).
  - The latest possible start date/time.
- For a missing/incomplete stop date/time, the later date/time of the following will be imputed:
  - The earlier date/time of: the latest possible stop date/time and the date/time of last dose of treatment (date/time of study completion or early termination).
  - o The earliest possible stop date/time.
- Here, the earliest possible date/time is defined as:
  - o The date/time itself if available.
  - The date/time of the first day of the month at 00:00hrs, if month and year are available but the day/time is missing.
  - The date/time of the first day of the year at 00:00hrs, if year is available but day/time and month are missing.
  - o 00:00hrs on the day of informed consent, if the date/time is completely missing.
- The latest possible date/time is defined as:
  - o The date / time itself if available.
  - The date / time of the last day of the month at 23:59hrs, if month and year are available but the day / time is missing.

Final Version 5.0 Page 31 of 76

The date / time of the last day of the year at 23:59hrs, if year is available but day / time and month are missing.

Protocol Number:

o 23:59hrs on the date of last known date on the study for the patient plus one year, if the date / time is completely missing.

#### 10 **DISPOSITION**

The number of patients screened, failed screening (patients who did not meet all eligibility criteria and was not randomized), enrolled (patients with informed consent and all eligibility criteria met or randomized), treated but not randomized, randomized (treated, and not treated with clinical trial treatment), completing clinical trial treatment (and reasons for not completing), and completing the clinical trial (and reason for not completing) will be presented in frequency tables by treatment group.

The number of patients in each analysis population (SAF, FAS, and PPS) will be summarized by treatment group. A by-patient listing of disposition will be provided.

All major protocol deviations will be presented as a frequency table by treatment group and in a by-patient listing for all randomized patients, which will include the category of the deviation, the deviation text, and whether the patient was excluded from PPS.

In addition, the counts on COVID-19 related major PDs will be provided, together with a by-patient listing for all COVID-19 related PDs.

In addition, a listing of the patients affected by Coronavirus Disease of 2019 (COVID-19) and their COVID-19 AE details will be provided for the FAS.

A table for the summary of stratification factors by treatment group for FAS and a separate listing of patients with mis-stratifications will be displayed.

#### 11 DEMOGRAPHICS AND BASELINE CHARACTERISTICS, AND DISEASE AND MEDICAL HISTORY

# 11.1 Demographic and Baseline Characteristics

All demographic, baseline characteristics, including azithromycin at randomization, and antibodyresponse data will be summarized by treatment group for SAF, FAS and PPS. For summary purposes, the most recent, non-missing result obtained on or prior to the baseline visit will be used.

Azithromycin at randomization will be derived by identifying azithromycin among medications collected in the study (generic name: azithromycin) using any of the following rules:

azithromycin is ongoing at the date of randomization (regardless of start date);

Final Version 5.0 Page 32 of 76 azithromycin start date is on the randomization date (regardless of end date).

By-patient listings will be provided for all demographic and baseline characteristics.

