#### Assessments:

Spirometry (FEV1, oclasse), and FVC) will be measured at all visits using the provided study on-site spirometer according to ATS/ERS 2005 guidelines.

Spirometry measurements on site will be performed by a registered respiratory therapist or certified pulmonary function technician who is blind to the patient's treatment assignment. Spirometry data will be reviewed by a blinded central reader, as described in the Vitalograh site manual.

Portable spirometers (CCI) will also be introduced at the screening visit for all patients newly enrolled under protocol version 3.0 or later. In addition to the Spirometry performed on the patients will perform spirometry using the ccl device at every on-site study visit ccl.

If patients cannot attend visits on site due to COVID-19, remote visits with guided home spirometry will be performed (FEV1, CCI), and FVC) using the ccl

For the determination of eligibility at Screening, only spirometry data obtained with the study column spirometer will be used.

For the evaluation of of BOS progression during the clinical trial period the further decline of FEV1 of  $\geq$  10% or  $\geq$  200 mL from baseline, absolute decrease in OCI of  $\geq$  5% must be

confirmed by measurements taken with **CCI** spirometer at least 2 weeks apart. Changes to standard of care are allowed at the investigator's discretion (e.g., changes in doses of immunosuppression, azithromycin, ATG, Photopheresis, leukotriene antagonists, cytostatics, irradiation therapy). All changes to SoC must be recorded in the eCRFs (Electronic Case Report Forms). All medically indicated procedures performed during the course of the clinical trial will be documented in the eCRFs. For assessment of patient survival, overall mortality, BOS-related mortality and non-BOS-related mortality will be taken into account at any time throughout the clinical trial period. Cumulative dose of immunosuppressants will be assessed throughout the Study for tacrolimus, MMF/equivalent, and corticosteroids. Quality of Life will be assessed at Visits 1, 4, 6, and 9/End of Treatment (EoT) when patients have to complete the EQ-5D-5L Questionnaire. Absolute and relative change from baseline will be calculated. Hospitalization will be assessed for overall number of days, days on regular ward, days in ICU, and days in ICU on ventilation.

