#### 9.3.1 Blinding

The pulmonary function technicians, respiratory therapists, or physiotherapists who conduct spirometry on site will be blinded to treatment assignment. Patients and other unblinded personnel will be asked to not share treatment assignment information with the pulmonary function technicians, respiratory therapists, and physiotherapists. The statistician who performed the interim sample size re-assessment was blinded to study treatment assignment. For details of the blinding of the Data Monitoring Committee members, see Section 13.2. For details of the blinding of the Adjudication Committee members, see Section 13.3. Clinical trial monitors, treating physicians, study nurses, study coordinators, and enrolled patients will not be blinded to study treatment assignment.

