#### 10 SELECTION AND WITHDRAWAL OF PATIENTS

#### 10.1 Patient Inclusion Criteria

- 1. Adult patients of  $\geq$  18 years who received a double lung transplant at least 12 months prior to Screening.
- 2. Patients with BOS diagnosis defined as CLAD-BOS phenotype with:
  - a) Screening  $FEV_1$  between 85-51% of personal best  $FEV_1$  value post-transplant. OR
    - b) Screening FEV1 >85% of personal best FEV1 associated with EITHER a  $\geq$  200 mL decrease in FEV1 in the previous 12 months OR according to medical history showing BOS progression.
- 3. Diagnosis of CLAD-BOS must be made at least 12 months after lung transplantation and
  - a) within 12 months prior to the screening visit.

OR

- b) more than 12 months from screening and patient must have shown a decline in FEV1 ≥ 200ml in the previous 12 months before screening, which is not due to acute infection or acute organ rejection.
- 4. Patients in whom the diagnosis of BOS has been confirmed by the elimination of other possible causes of obstructive or restrictive lung disease (CLAD RAS phenotype, see Protocol Specific Definitions).
- 5. Patients should be on a drug maintenance regimen of immunosuppressive agents including tacrolimus, a second agent such as but not limited to MMF or azathioprine, and a systemic corticosteroid such as prednisone as third agent. The regimen must be stable within 4 weeks prior to randomization with respect to the therapeutic agents. In case a patient is also receiving concomitant azithromycin for prophylaxis or treatment of BOS, in addition to the previously described immunosuppressive regimen, azithromycin must be on a stable regimen for at least 4-weeks prior to randomization.
- 6. Patients capable of understanding the purposes and risks of the clinical trial, who have given written informed consent and agree to comply with the clinical trial requirements/visit schedules, and who are capable of aerosol inhalation. Patients must consent to retrieve prespecified data from the historic medical record (e.g., information related to the transplant surgery; spirometry data; medication use).
- 7. Women of childbearing potential must have a negative serum or urine pregnancy test within 7 days prior to randomization and must agree to use one of the methods of contraception listed in Appendix II through their End of Study Visit.
- 8. Patients have no concomitant diagnoses that are considered fatal within one year (12 months) of Screening.

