#### 11.3.3 Azithromycin

Patients receiving azithromycin prior to randomization (for prophylaxis or treatment of BOS), must be on a stable regimen for at least 4 weeks prior to randomization. These patients can continue to receive azithromycin during the clinical trial as deemed appropriate by the investigator.

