### 14.1.3 Analysis Model

The primary efficacy analysis will be carried out using a LMM for repeated measurements, using all observed available  $FEV_1$  measurements. In case of death or re-transplantation events,  $FEV_1$  will be imputed as zero at each nominal day post event.

The dependent variables are the absolute change from baseline of FEV1 measurements at visit 2 (i.e., the first post-baseline visit) through visit 9 (Week 48). For the definition of baseline FEV1 please refer to section 8.1.1.

A flexible and robust model will be chosen for the random part of the LMM according to a prespecified stepwise procedure (see next section). The fixed part of the LMM is specified as follows: the model will contain (except from the intercept) time cubic splines, treatment, the interactions of time splines by treatment, baseline FEV1, the interactions of time splines with the baseline FEV1, region (North America versus all other countries together), age (< 55 versus  $\ge 55$  years), and use of azithromycin at randomization (i.e. Baseline, Visit 1).

The primary efficacy parameter will be estimated from the model by the adjusted difference between treatment groups in mean FEV1 change from baseline after 48 weeks. The p-value for the null hypothesis of no difference and a two-sided 95% confidence interval for the difference will be provided.

Superiority of L-CsA will be demonstrated by a statistically significant result (defined as p<0.025, one-sided) in favor of the L-CsA plus SoC treatment compared to SoC alone.

The above comparison between treatment groups at all the other visits (2-8) will also be presented.

A figure of observed mean change from baseline and standard errors at each visit, by treatment group will be presented. A figure with adjusted mean changes from baseline at each visit by treatment group derived from the LMM will be provided.

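### SAP 11.1 codes azithromycin started on the day of randomization as baseline use, so a decision made after open-label allocation can enter the primary model as a baseline covariate

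*SAP*

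**What the plan says.** SAP 11.1 sets the flag to Yes "using any of the following rules". The first rule is "azithromycin is ongoing at the date of randomization (regardless of start date"; the second is "azithromycin start date is on the randomization date (regardless of end date". Either is enough. Neither uses a clock time or asks whether the start came before randomization.

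SAP 14.1.3 puts this flag into the primary LMM as "use of azithromycin at randomization (i.e. Baseline, Visit 1". It is also used in:
- the two imputation models (SAP 14.2.1 and 14.2.2);
- the MMRM (14.2.3) and, through the shared covariate list, the ANCOVA (14.2.5);
- the piecewise regression (14.3.3.2);
- a subgroup (14.6).

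On conduct, Protocol 9.3.1 places treating physicians among those who know the allocation; the same sentence says that "study coordinators, and enrolled patients will not be blinded to study treatment assignment". The synopsis states "Changes to standard of care are allowed at the investigator's discretion", and Protocol 11.3 counts azithromycin use as SoC. For eligibility, criterion 5 of Protocol 10.1 says that "azithromycin must be on a stable regimen for at least 4-weeks prior to randomization", for patients already taking it for BOS.

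**The concern.** A covariate is safe to adjust for if treatment assignment cannot have influenced it. Azithromycin begun on the randomization date fails that test whenever it was begun after the allocation was disclosed. A physician whose patient is assigned SoC alone may add azithromycin that day, and the derivation then describes the patient as a baseline user.

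The SAP is stricter in two comparable places. Section 8.1.1 takes only the pre-randomization FEV1 from Visit 1. Section 13 separates prior from concomitant medication by date and time of randomization, so a start after allocation is concomitant there but baseline in 11.1.

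At stake is a small directional error in the primary contrast. SAP 14.1.1 keeps FEV1 data after augmentation of SoC, so the effect of such changes is meant to stay in the comparison. Adjusting for some of them as if they were baseline takes part of that effect out.

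**Working it through.** **Plan's own figure.** SAP 8.2 gives a difference of 200 mL, SD 350 mL, one-sided alpha 0.025, and at least 80% power with 50 per arm. Normal approximation: n = 2 × (1.960 + 0.842)² × (350/200)² = 48.1, so 49 per arm. The t-test calculation gives 49.05, rounded up to 50, with power 80.8% at 50. The figure reproduces, and this point does not change it.

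**Can a post-allocation start reach the model?**
1. A start on the randomization date satisfies rule 2 whatever its clock time.
2. If use continues, the same record may also satisfy rule 1, so deleting rule 2 alone does not close the route.
3. The allocation is known to the treating physician at Visit 1, and SoC changes are permitted.
4. The flag is a fixed effect in the primary LMM.

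**Size.** Inputs from the documents: SD 350 mL, effect 200 mL, 169 randomized (SAP 8.2), 1:1 allocation (Protocol 9.3), hence about 84.5 per arm. Assumed, because the documents do not give them:
- p0, the share already on azithromycin: 50-80%;
- γ, the FEV1 effect of azithromycin: 100-200 mL, the same for prior use and same-day starts;
- pC and pT, the same-day start rates among non-users in the SoC and L-CsA arms: pC 5%, 10% or 25%, pT 0.

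The approximate difference between the estimate with the SAP flag and the estimate with a strictly pre-randomization flag is γ × (1 − p0) × (pC − pT). A simulation of a simplified Week 48 linear model (169 patients, 3,000 runs per scenario) gives the gaps in parentheses.

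| γ (mL) | p0 | pC 5% | pC 10% | pC 25% |
|---|---|---|---|---|
| 100 | 80% | 1.0 (1.0) | 2.0 (2.0) | 5.0 (5.1) |
| 100 | 50% | 2.5 (2.5) | 5.0 (5.0) | 12.5 (12.6) |
| 200 | 80% | 2.0 (2.0) | 4.0 (3.8) | 10.0 (9.8) |
| 200 | 50% | 5.0 (4.9) | 10.0 (10.2) | 25.0 (25.2) |

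Example: γ = 200, p0 = 50%, pC = 10%. The expected number of SoC same-day starters is 84.5 × 0.5 × 0.10 = 4.2. The treatment difference that retains SoC changes is 200 − 10 = 190 mL. The SAP flag gave 202.1 mL on average and the strict flag 191.9 mL. With 10% starting in both arms (p0 = 50%, γ = 200), both flags gave 200.8 mL against a true 200.

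**Scale.** The standard error is about 350 × √(2/84.5) = 54 mL. A 10 mL shift is 10/54 = 0.19 standard errors; 25 mL is 25/54 = 0.46.

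**The case against.** **The route is hypothetical.** No same-day start is reported, and Protocol 14.2.2 has sites stress to both arms adherence to the medications taken before the trial, which works against same-day changes. The SAP 14.3.4 t-test has no azithromycin term, so this coding cannot affect it. All of this stands and limits the weight of the point. It does not repair the rule: the t-test is supplementary, and the covariate is in the primary model.

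**A reader might infer that rule 2 contradicts the four-week stability requirement.** It does not. Protocol 11.3.3 restates that requirement for patients who already take azithromycin for BOS. It governs the eligibility of existing users; it neither defines the covariate nor bars a later start. The protocol's own covariate (15.2.3.1) is use at randomization, with no minimum duration.

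**A reader might infer that every same-day record is a first start or an eligibility deviation.** The rule works on medication records. A record dated that day could be a new entry, such as a dose change, for a long-term user.

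**A reader might extend the criticism to starts shortly before randomization and ask for a 28-day cut-off.** A start before allocation cannot respond to it, so it does not open this route. Such a cut-off would also code some current users as No.

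**Imputed dates might seem to widen the problem.** The convention in SAP 9.5.3.2 can place a missing start date on the randomization date, but 9.5.2 restricts imputed dates to other purposes, so this is not established.

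**Conclusion.** The point holds in a limited form. As written, SAP 11.1 lets a treatment decision taken after open-label allocation be coded as a baseline covariate in the primary analysis, and this is out of line with SAP 8.1.1 and 13.

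The likely size is small: about 1-10 mL if 5-10% of SoC non-users and no L-CsA non-users start that day, and up to about 25 mL at 25%, against a standard error of about 54 mL. These ranges rest on assumed start rates, prior use and azithromycin effect, and on a single-time-point model in place of the full LMM. The direction toward L-CsA requires that starts cluster in the SoC arm and that azithromycin preserves FEV1. With no such starts, or equal rates in the arms, the shift is zero. A reader might infer that the primary result is in serious doubt; the documents do not support that. Sample size and alpha are unaffected. The change is worth making because the possible error is directional and cheap to remove.

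**What to change.** In SAP 11.1, delete the second rule and reword the first as: *azithromycin started before the randomization date (or before the randomization date/time where time is recorded) and ongoing at randomization*. In addition:
- Link consecutive azithromycin records, so that a long-term user with a new record on that day stays Yes.
- Treat starts on or after randomization as post-randomization SoC changes, with FEV1 data kept in the primary analysis.
- List same-day starts by arm, so that a reader can see whether the issue arose.
- Use this one variable throughout SAP 14.1-14.3 and 14.6.

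A version requiring at least 28 days of prior use may be reported as a sensitivity analysis but should not replace the covariate.

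**Cost.** One derivation edit before database lock, using medication dates already collected; no new data and no change to the sample size. The downside is that a same-day start made before randomization is coded No if no time was recorded.

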### 11.2 Disease and Medical History

Details of History of BOS diagnosis eCRF page [FVC (absolute), FVC - % of personal best post-transplant, FEV1 (absolute), FEV1 - % of personal best post-transplant, CCI (absolute), CCI - % of personal best post-transplant and FEV1/FVC (ratio)], details of Historical Spirometry eCRF page [FVC (absolute), FEV1 (absolute), CCI (absolute) and FEV1/FVC (ratio)] as well as details related to each patient's lung transplant as recorded in the Lung Transplantation History eCRF page [type of underlying indication for lung transplant, time between lung transplantation and onset of BOS, donor gender, cytomegalovirus (CMV) status donor, CMV status recipient, Epstein Barr Virus (EBV)-status donor, EBV-status recipient, receive induction therapy, receive antiviral/antifungal/antibacterial therapy, cold ischemia duration double lung] will be summarized by treatment group for SAF, FAS and PPS.

Disease history, including the details from the Risk Factors eCRF will be listed by FAS.

Time (days) between lung transplantation and onset of BOS is defined as the duration between date of lung transplantation and onset of initial BOS + 1.

All other significant medical conditions (including gastro-esophageal reflux disease) and procedures (including past surgeries) occurring before the informed consent form is signed will be recorded as medical history.

Medical history will be coded using the Medical Dictionary for Regulatory Activities (MedDRA) [Version 23.1] and will be presented by Internationally Agreed order System Organ Class (SOC) and Preferred Term (PT) and total. The SOCs and PTs are to be sorted by SOC and descending PTs.

Medical history will be summarized by treatment group and overall for the SAF, FAS and PPS as follows:

- The number and percentage of patients with at least one medical history record will be presented.
- The number and percentage of patients with at least one medical history record within each primary SOC and PT will be presented. The summary will be sorted using the internationally agreed order for SOC and using descending order of overall numerical counts for PT. Where terms tie, these will be sorted alphabetically.

Medical history records will be listed by-patient and within-patient by medical history start date for the FAS.

Final Version 5.0 Page 33 of 76

